7.1 Clinic Visit

All data collection for an individual participant will be conducted on a single day. It is anticipated that the visit will take several hours to complete. Participants will be asked to fast for 12 hours before coming to the clinic. After a urine pregnancy test and venipuncture, the participant will be weighed and her height will be measured. She will be fed a standard meal, complete questionnaires, bone density will be measured by DEXA, breast density will be measured by MRI, and an in-person 24-hour dietary recall will be conducted. Two additional 24-hour dietary recalls will be conducted by telephone in the following 2 weeks. Trained and certified individuals who are masked to treatment assignment will perform all data collection.

We will pay transportation costs for participants who live out of town. For participants who have to fly, one night lodging will be provided. Participants who have moved and live closer to a different DISC clinical center will have the option of going to that center for evaluation. Participants who attend the clinic visit be reimbursed \$500 for participating in this very involved study.

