7.10.1 MRI Procedure

Each subject will be imaged in a whole body 1.0 Tesla or higher field strength MRI scanner using a dedicated breast imaging radiofrequency coil. The subject will lie prone on the table with both breasts hanging freely in the coil. The following pulse sequences will be performed in the transaxial orientation with a 32-40 cm field-of-view for bilateral coverage:

1. 2D or 3D spin echo or gradient echo localization sequence; 32-40 cm field of view (FOV), 5 cm slice thickness, number of locations to cover both breasts in I/S direction.

- 2D T2-weighted fast spin echo sequence; TR/TE = 5500 ms/85 ms, 24 slices, 3-4 mm slice thickness to cover both breasts in I/S direction, echo train length 8, 32-40 cm field of view (FOV), 512x256 matrix, Frequency A/P.
- 3. 3D fast gradient echo sequence without fat-saturation; TR/TE = 20 ms/minimum TE with Fat/Water in phase, 30 degree flip angle, FOV 32-40 cm, 60 slices, 1-2 mm slice thickness to cover entire breast in I/S direction, 512-256 matrix, frequency A/P.
- 4. 3D fast gradient echo sequence with fat-saturation; Repeat #3 with chemical saturation fatsuppression.

No contrast agent will be administered for this examination. Additional pulse sequences including diffusion-weighted and 3D steady state free procession sequences may be acquired depending on availability of these techniques on the MRI systems at the participating sites. The total exam time, including patient positioning will be less than 1 hour. Subjects are given the opportunity to lie in the magnet before scanning begins. Those subjects experiencing claustrophobia are counseled by a technologist or physician and will not be pressured to finish the exam. Earplugs are provided to each subject to reduce noise levels.

All MRI exams will be performed during the luteal phase of the menstrual cycle. Although diagnostic breast MRI is usually scheduled in the follicular phase of the menstrual cycle because it is easier to detect tumors, we will be using MRI to measure physiological characteristics of the breast, not to detect tumors or other abnormalities. Because non-contrast MRI scans to be used are not diagnostic, we do not anticipate detecting abnormalities. However, if abnormality is detected, the participant will be informed and the results will be sent in writing by the clinical center PI to the physician identified by the participant on the consent form.

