7.11.1 Scan Protocol

The participant will be asked to disrobe and wear a hospital gown. (Buttons, heavy fabrics, bra clasp, etc., can all cause inaccurate results.) They will then lie down on the table of the DEXA device. This is typically a simple padded tabletop. The x-ray arm will make several passes over the patient for each scan mode. The following scans will be acquired:

- 1. Lumbar Spine: A/P or P/A view, default scan speed, L1 L4.
- 2. Proximal Femur: A/P or P/A view, default scan speed.
- 3. Whole body: default scan speed

The scan combination of dedicated proximal femur, lumbar spine (L1-L4), and whole body DEXA scans is important for this study for several reasons. Dedicated scans of the lumbar spine (L1-L4) and of the proximal femur are the most widely used combination for diagnosing osteoporosis and assessing fracturing risk since fractures at these sites (1) are best predicted by site-specific scans, and (2) these fractures have the highest morbidity. Bone density measures at these two sites will allow for direct comparison of these study results to most of the osteoporosis literature. The spine contains a high percentage of trabecular, or spongy, high turnover bone (66%) while the proximal femur contains more of a mix of trabecular and cortical (compact) bone. The whole body is comprised of 80% cortical bone. It is a measure of systemic bone health and responds slower to changes in bone turnover. Thus, it may contain more "memory" of the intervention than the localized spine and femur sites. The entire examination should take less than 30 minutes. Any of the currently manufactured DEXA devices from Hologic, Inc., or GE/Lunar are appropriate.

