7.11.5 Quality Assurance Program

Since the study needs to be sensitive to even small changes bone density, a comprehensive quality assurance program has been included. DEXA devices can have calibration drifts or major service issues over the course of the study. However, it is possible to correct for these calibration drifts posthoc if appropriate phantoms are scanned as part of the protocol. The phantoms of choice for this study are the device-specific spine phantoms (come with each device and different for each manufacturer) and the Hologic Whole Body phantom. These phantoms accurately predict the in vivo calibration of the device such that changes in the phantom measures are used to directly correct participant data collected during that interval. The spine phantom is typically scanned once a day as standard practices at most clinical DEXA sites. The whole body phantom is critical since previous work by the UCSF investigators has shown that the typical spine quality control program does not predict the whole body calibration. The whole body phantom would be scanned 3 times a week. The UCSF investigators will use Cumulative Sums (CUSUM) statistics to determine when a change in the calibration has occurred [144].

DEXA participant scans will be acquired at each of the 6 clinical sites. To pool scan results from different DEXA devices, static calibration differences must also be corrected. Ideally, this is done by scanning the same individuals on all devices. However, this is impractical. We will circulate a single set of calibration phantoms to all sites. This set of phantoms is more complete than the daily phantoms and made available by the UCSF investigators. Machines of the same make and model will be readily cross calibrated using this phantom data. Devices from different manufacturers will be calibrated with in vivo calibration equations from the literature. The calibration and monitoring activities will be coordinated by one of our investigators from UCSF ([name]) who is an expert in this area. The DEXA cross calibration protocol will take about 1 hour, and be done once during the course of the study.

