12.2 Data Analysis

All analyses will be performed using analysis files created by adding follow-up data to the main DISC database with verification by manual checking. SAS (SAS Inst., Cary, NC) will be the primary software used for analysis supplemented with S-Plus (Insightful Corp., Seattle, WA) and Stata (Stata Corp., College Station, TX).

Because DISC was a clinical trial, analysis of the specific aims will be performed by randomized treatment assignment. Mean serum progesterone will be compared between the intervention and usual care groups without regard to compliance with the intervention, attendance at intervention sessions, or attendance at earlier DISC clinic visits. Because hormonal contraceptives contain progesterone, only women not using hormonal contraceptives will be included in analysis of treatment group differences in serum progesterone levels. The distribution of serum progesterone values will be examined to determine whether transformation is appropriate prior to analysis. In previous DISC analyses, we In transformed hormone concentrations to improve normality and decrease dependence of the variance on concentration. We anticipate that In transformation of progesterone data collected at the proposed follow-up visit will also be appropriate, but a final decision will be made after examining the data. The analytical approach will depend on the distributions of age, race, and menstrual cycle day when blood was collected at the clinic visit in the two treatment groups. These characteristics are potential confounders that would not be affected by the intervention. If the treatment groups are balanced on these characteristics, means can be estimated directly and statistical significance of the treatment group differences can be tested using a Student's t-test. If the participants in the treatment groups are not balanced on these characteristics and there is evidence for confounding, we will estimate adjusted means and test for statistical significance using linear models. We used analysis of covariance to compare adjusted treatment group means in previous DISC hormone analyses.

The effect of missing progesterone data on observed treatment group differences will be evaluated using the multiple imputation method of Rubin [89], in which multiple datasets are constructed, analyzed, and results combined so that the underlying variability of the outcome is preserved.

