In secondary analysis of the primary aim, we will determine whether treatment group differences in progesterone are related to differences in several individual characteristics including age at menarche, BMI, and % body fat by including appropriate covariates in linear models. We will investigate if there is a particular component of the diet intervention (energy, total or saturated fat, fiber) responsible for observed differences in progesterone levels. BMI and diet at time of the follow-up visit or earlier, during puberty, could be responsible for observed treatment group differences in progesterone at the follow-up visits. To evaluate if puberty is a critical time for exposure, we will estimate the mean level of exposure at earlier DISC visits and use linear models to evaluate whether

average pubertal exposure can explain treatment group differences in progesterone levels at the follow-up visit. Furthermore, we will evaluate potential confounding and effect modification of treatment group differences in progesterone levels at follow-up visits by changes in characteristics such as diet, anthropometry, and physical activity between the last DISC visit and the follow-up visit and by intervening events such as pregnancy, lactation, and use of hormonal contraceptives, by including terms for main effects in models to evaluate confounding and by including cross-product terms in models that include main effects to evaluate effect modification.

Analysis of secondary aims will be performed using the same approach as described for the primary specific aim except breast MRI analysis will use statistical techniques for paired organs as described below. Similar to progesterone, women using hormonal contraceptives will not be included in analysis of serum estradiol. We will, however, perform breast MRI and bone densitometry on these women. In analysis of treatment group differences in breast density and bone density, we will evaluate confounding by past and present hormonal contraceptive use. We also will test for interaction of hormonal contraceptive use with treatment group effects by including cross-products terms in models. Analyses will be stratified by hormonal contraceptive use if cross-product terms are significant.

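### The bone and breast density analyses include no term for the clinic or scanner that made the measurement, which costs some precision, mainly for breast density

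*Protocol*

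**What the plan says.** **Analysis rule.** For the primary aim, Protocol section 12.2 says: "The analytical approach will depend on the distributions of age, race, and menstrual cycle day when blood was collected at the clinic visit". If the arms are balanced on these characteristics, a Student's t-test is used. If they are not, and there is evidence for confounding, adjusted means come from linear models. For the other aims: "Analysis of secondary aims will be performed using the same approach as described for the primary specific aim". The exception is breast density, which is analysed by GEE to allow for two breasts per woman.

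**Further covariates for bone and breast density.** Section 7.11.4 brings in percent body fat. Section 12.2 adds past and present hormonal contraceptive use, with an interaction test. Section 12.2 nowhere names clinic, scanner, make or field strength.

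**Bone measurement.** On equipment, section 7.11.1 says: "Any of the currently manufactured DEXA devices from Hologic, Inc., or GE/Lunar are appropriate". Section 7.11.5 says: "DEXA participant scans will be acquired at each of the 6 clinical sites". The same section recognises the consequence: "To pool scan results from different DEXA devices, static calibration differences must also be corrected". Phantoms are used to correct drift, and a circulated phantom set cross-calibrates machines of the same make and model. Across makers: "Devices from different manufacturers will be calibrated with in vivo calibration equations from the literature". One investigator analyses all scans (section 7.11.2).

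**Breast measurement.** Section 7.10.1 says: "Each subject will be imaged in a whole body 1.0 Tesla or higher field strength MRI scanner". The safeguards are technologist training, site certification on five volunteers, phantoms to test the sequences (section 7.10.5) and a single analyst (section 7.10.2). No adjustment of density values between scanners is described.

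**Where women are scanned.** Under section 7.1, participants who have moved and "live closer to a different DISC clinical center will have the option of going to that center".

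**The concern.** The decision rule was written for serum progesterone, which one central laboratory assays in batches balanced on treatment group (section 7.9). Bone and breast density are different, because the measuring instrument is local to the site. The rule checks the cycle day of the blood draw before bone density is analysed, but never checks which machine produced the value.

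If scanners or clinic populations differ, that variation sits in the residual and widens the confidence interval for the treatment difference. For bone the margin is narrow: section 12.3.3 puts the target difference at 2.5-2.6% of the mean, and section 7.11.5 itself asks for sensitivity to small changes. For breast density there is no stated correction to reduce scanner differences before analysis.

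**Working it through.** **Inputs from the protocol**
- Women per group: 108-122 (section 12.3.2).
- Total body BMD: SD 0.08 g/cm2, mean 1.16; stated detectable difference .029-.030.
- Percent dense breast tissue: SD 17.7 points; stated detectable difference 6.3-6.7.
- Two-sided 5% test (stated for Table 1) and 80% power, so K = 1.960 + 0.842 = 2.8016.
- Six DEXA sites (section 7.11.5). I assume the same six for MRI.

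**Step 1: reproduce the plan.**
- Women per group = 301 x participation x 0.9 / 2, which is 108.4 at 80% participation and 121.9 at 90%.
- Detectable difference = K x SD x sqrt(2/n).
- BMD: 2.8016 x 0.08 x sqrt(2/108) = .0305; at n = 122, .0287.
- Breast density: 2.8016 x 17.7 x sqrt(2/108) = 6.75; at n = 122, 6.35.

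These agree with the stated figures to rounding. The calculation has no separate clinic or device component.

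**Step 2: add an assumed between-site component.** The protocol gives no such variance, so these SDs are assumptions. Here the planning SD is taken as within-site, and total SD = sqrt(SD^2 + site SD^2).

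| Outcome | Assumed site SD | Total SD | Detectable difference, n = 108 |
|---|---|---|---|
| BMD | 0 | .0800 | .0305 |
| BMD | .02 | .0825 | .0314 |
| BMD | .03 | .0854 | .0326 |
| Breast density | 0 | 17.7 | 6.75 |
| Breast density | 4 | 18.1 | 6.9 |
| Breast density | 6 | 18.7 | 7.1 |

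The BMD assumption is .02/1.16 = 1.7% to .03/1.16 = 2.6% of the mean.

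**Step 3: power at the planned difference.** Power = Phi(K x SD / total SD - 1.960).
- Breast density, site SD 4: 2.8016 x 17.7/18.15 - 1.960 = 0.773, power 78%.
- Breast density, site SD 6: 2.8016 x 17.7/18.69 - 1.960 = 0.693, power 76%.

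**Step 4: vary the assumption.** Let the site share of total variance be s, so total SD = SD / sqrt(1 - s). Power at n = 108 is 79%, 78%, 76%, 71% and 65% for s = 2%, 5%, 10%, 20% and 30%. Site SDs of 4 and 6 points correspond to shares of about 5% and 10% (16/329.3 and 36/349.3).

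**Step 5: the other reading of the planning SDs.** If they already contain between-site variance, adjustment improves on the plan. At s = 10% the detectable differences become .0305 x sqrt(0.9) = .0289 and 6.75 x sqrt(0.9) = 6.40. Adjustment helps under either reading whenever s is not negligible.

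**Step 6: price of the factor.** Six sites use 6 - 1 = 5 degrees of freedom. With 216 women in two arms, residual degrees of freedom go from 214 to 209.

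**The case against.** The strongest reply is that a full covariate list usually belongs in the statistical analysis plan, which is not at hand, and that the loss is small and rests on assumed variances. The second half stands: the range used is not sourced in the protocol and the effect is a few points of power. The breast-density SD itself comes from 15 women, so its own 95% interval under normality (about 13 to 28) dwarfs a shift from 17.7 to 18.1-18.7. The worst-case BMD SD of .085 is below the .087 that section 12.3.2 already calls comparable. These are secondary aims, with power given for information. The first half does not fully answer the point: section 12.2 does not leave the model open but fixes a rule and its balance criteria, and carries them over to outcomes measured on local machines.

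Several stronger readings are tempting and are not supported:
- **That the models adjust only for age, race and cycle day.** Percent fat and contraceptive use are also considered, and the first three enter only if unbalanced and confounding.
- **That DEXA device differences go uncorrected.** Section 7.11.5 corrects drift and static differences before analysis.
- **That the sites do use different makes or field strengths.** The protocol permits this; it does not say it happens.
- **That hormone models also need a clinic term.** One laboratory and balanced batches give no ground for it.

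**Conclusion.** The point holds as a modest loss of precision, chiefly for breast density, where no between-scanner correction is stated. For BMD what can remain is residual calibration error, most plausibly across makers, together with differences between clinic populations.

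On the assumed site SDs, the detectable difference rises by about 3-6% for breast density (6.9/6.75 to 7.125/6.75) and 3-7% for BMD (.0314/.0305 to .0326/.0305). The loss would be material only if site accounted for something like 20-30% of the variance, and nothing in the protocol says that it does.

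A reader might infer that the treatment comparison is biased, since women can choose another centre and not all will attend. The documents do not support that. Allocation was random, data collectors are masked, one investigator analyses all scans of each type, and nothing suggests that relocation or attendance differs by arm.

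**What to change.** Before any comparison by arm, specify the clinic/scanner where the scan was made as a fixed factor in the breast-density GEE and in the BMD linear model, whether or not the arms look balanced on it. State how differences in MRI scanner and field strength are to be handled. Do not use blood-draw cycle day as a balance criterion for BMD. It can stay for breast density, because scan and blood draw fall on the same day and section 7.5 treats menses timing as relevant to the MRI data. No clinic term is needed in the hormone models.

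The cost is about 5 degrees of freedom out of more than 200, and more if a device is replaced within a clinic and needs its own level. One caution applies: the scan centre can be chosen after randomisation, whereas section 12.2 favours covariates that the intervention would not affect. The distribution of scanning centre by arm should therefore be reported beside the adjusted result.

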12.3 Sample Size and Power

Participants in the proposed study are the 301 female DISC participants. Because this is an existing cohort and sample size is set, we estimated detectable differences in luteal phase progesterone levels (our primary specific aim). For information, we also provide detectable differences for our secondary specific aims. Detectable differences in treatment group means were calculated using S-Plus 2000 (Insightful, Seattle WA).

12.3.1 Primary Specific Aim

We used data from the DISC last visit on serum progesterone levels in 9 usual care group participants whose blood was collected 1-6 days before the start of their next menses. This time frame is the window during which follow-up visits will take place in the proposed study. Earlier DISC analyses were performed on In transformed hormone values. We also used In transformed values to improve normality of distribution for these power calculations. The mean transformed progesterone concentration adjusted for age and cycle day was 6.76 (sd = 0.52). Hormones will be measured only in participants not using hormonal contraceptives. CDC estimates that 40% of women 20-24 years old use hormonal contraceptives [146]. In our pilot study of DISC participants, 48% of women reported using hormonal contraceptives and 10% were pregnant. Ninety-three percent of participants in our pilot said they would be willing to come to a follow-up visit. We estimated detectable differences in progesterone concentrations at 80% (conservative) and 90% participation rates assuming 50-60% of participants are using hormonal contraceptives or pregnant and cannot be included in these analyses (Table 1). Depending on participation rate, hormone use, and pregnancy we will be able to detect

Table 1. Minimal Detectable Differences For Luteal Phase Progesterone and Estradiol at α =.05 (2-sided) and 80% Power

| Participation Rates | Hormonal Contraceptive Use or Pregnant | Number per Group | Detectable Difference Progesterone | | Detectable Difference Estradiol | |
|------------------------|--|---------------------|---------------------------------------|---|------------------------------------|---|
| | | | In | % | In | % |

| 80% | 50% | 60 | .266 | 23.3% | .164 | 15.1% |
|-----|-----|----|------|-------|------|-------|
| | 60% | 48 | .297 | 25.7% | .183 | 16.7% |
| 90% | 50% | 68 | .250 | 22.1% | .154 | 14.3% |
| | 60% | 54 | .280 | 24.4% | .173 | 15.9% |

22%-26% lower progesterone levels in the intervention group compared to usual care ((e $^{6.76}$ – e $^{6.76}$ - $^{2.266}$)/e $^{6.76}$). At last DISC visits the intervention group's mean progesterone level was 52.9% lower than the usual care group. We will have ample power to detect a difference that is less than half as large as this.

12.3.2 Secondary Specific Aims

Luteal Phase Serum Estradiol: We used data from the DISC last visit on serum estradiol levels in 9 usual care group participants whose blood was collected 1-6 days before the start of their next menses. The mean In transformed estradiol concentration adjusted for age and cycle day was 2.62 (sd=.32). We estimated detectable differences in estradiol concentrations at 80% and 90% participation rates and assuming 50% -60% of participants are using hormonal contraceptives or pregnant and cannot be included in these analyses (Table 1). We will have 80% power to detect 14%-17% lower estradiol levels in the intervention compared to the usual care group.

Bone Mineral Density: We used data from Teegarden [147] to estimate the detectable differences in total body bone mineral density. Teergarden used DEXA to measure total body bone mineral density in 215 women 18-31 years old (mean age = 23.8 years). Their mean total body bone mineral density ranged from 1.00-1.37 gm/ cm² with a mean of 1.16 gm/cm² (sd = .08). This standard deviation is comparable to the population standard deviation of .087 in the Hologic Reference Data. With 80%-90% participation rate and 10% excluded because of pregnancy, we will have DEXA data on 108 – 122 women per group. This yields 80% power to detect treatment group differences in total body bone mineral density of .029 - .030 gm/cm².

Breast Density: We used data from Lee [95] to estimate detectable differences in percent dense (fibroglandular) breast tissue in intervention vs. usual care group DISC participants. Lee measured fatty and fibroglandular tissue volumes by MRI in the breasts of 40 women 20-83 years old. Because breast density changes with age and menopausal status and all DISC participants at follow-up visits will be 25-29 years old and premenopausal, we only used data from 15 women 20-45 years of age. Their percent dense tissue ranged from 18% - 83% with a mean of 45.1% (sd = 17.7%). With 80%-90% participation rate and 10% excluded because of pregnancy, we will have MRI data on 108 - 122 women per group. This yields 80% power to detect treatment group differences in percent dense breast tissue of 6.3% - 6.7%.

